Cover Page for Study Protocol

Sponsor-Investigator:	[name]	
NCT Number:	NCT03505476	
Unique Protocol ID:	201801808	
Official Title:	Optimizing the Previs Device for	
	Prediction of Postoperative Ileus	
Date of Document:	28 September 2020	

Device Name:	Previs Device
Title of Study:	Optimizing the Previs device for Prediction of Postoperative Ileus (Previs Optimization)
Study Center:	University of Iowa
Estimated number of subjects:	475 subjects (50% male, 50% female) will be recruited and enrolled in this study.
Study Period:	February 2018 until completion
Estimated date of first enrollment:	February 2018 will be the earliest day of enrollment, pending approval from UI IRB.
Estimated date of last enrollment:	We estimate that all subjects will be enrolled by January 2020.
Sponsor:	Entac Medical, Inc.
Version:	4.0
Date:	September 28, 2020

Table of Contents

I.	Statement of Compliance:
II.	IRB Oversight:
III.	Location of Study Procedures:
IV.	Trial Design:
V.	Study Aims:
VI.	Main Screening Criteria:
VII.	Screening/Recruitment procedures:
VIII.	Inclusion Criteria:
IX.	Exclusion Criteria:
X.	Study Procedures:
	Table 1. Study Procedures: 10
XI.	Possible Risks of the Study:
XII.	Adverse Event Reporting:
XIII.	Data Management:
XIV.	Primary End points:
XV.	Payment for Participation:
XVI.	Subject Safety:
XVII.	Statistical design plan:

I. Statement of Compliance:

This study will be conducted in compliance with the protocol, Good Clinical Practice and the applicable Food and Drug Administration and other Department of Health and Human Services regulatory requirements.

All key personnel (all individuals responsible for the design and conduct of this study) have completed Human Subjects Protection and Good Clinical Practice training.

II. IRB Oversight:

Human Subjects Office / IRB J. [name] [name] FWA#: FWA00003007 Voice: [contact] [contact] Email: [contact]

III. Location of Study Procedures:

University of Iowa Hospitals and Clinics (UIHC) [name]

IV. Trial Design:

This is a prospective, non-randomized, open label, single center study designed to assess and optimize performance of the Previs device.

V. Study Aims:

The aims of this study are:

1) To incorporate digital signal processing algorithms and design changes from prior trials into a re-designed prototype, self-contained, noninvasive device that retains or improves the predictive accuracy.

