- Inability to have prototype device applied to their abdominal wall due to a condition (ie: fistulas, stomas, drains, etc).
- Patients who develop documented evidence of intraperitoneal infection or urinary tract infection within 14 days of surgery will be excluded from analysis for primary outcome (but data will undergo analysis for potential detection of secondary ileus)

X. Study Procedures:

- Potential subject is approached at preoperative visit to discuss study, if interested.
- Informed consent signed.
- Previs device is applied either in the operating room at the completion of surgery or in the recovery room.
- Time and serial number of device application will be logged into study register.
- Study team member will administer Instrument Questionnaire daily, while hospitalized, for up to 10 days.
- Study team member will remove the Previs device 10 days post-operative or at subject discharge from the hospital.
- Study team will monitor the medical record and talk with subject for 14 days to collect any data related to a possible infection (intraperitoneal or urinary tract infection).
- Study team member will contact the subject 14 days post-operative to administer Instrument Questionnaire.
- Study team will review the subject's medical record to assess for any evidence of hospital readmission within 30 days of discharge.

Table 1Schedule of events

Event	Screening Visit	Day of Surgery (Day 1)	Day 2,3,4,5,6,7,8,9,10	14 Day Follow-Up
Informed Consent	Х			
Medical History	Х			
Medical Record		X	X	X
Review				
Review of	Х			
inclusion/exclusion				
criteria to confirm				
subject eligibility				
Device placement		X		
Device removal			X ^a	
Instrument		X	X	X
Questionnaire				

Adverse events	Х	Х	Х
monitoring			

a. At day 10 post-operative or discharge, whichever comes first.

XI. Possible Risks of the Study:

Risk of skin irritation where the device is placed. To minimize the risk of skin irritation, subjects will not be enrolled who have allergies to any of the device components or the adhesives that will be used. Study members will also monitor the device placement to ensure there is no irritation.

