During the course of a study, researchers may become aware of new information that would impact a subject's decision to participate, or continue participating in the research study. For example, interim analyses of data may identify a trend which impacts the safety of subjects, or may identify early efficacy (benefit) of one of the interventions under study. In addition, results from other research studies or changes in standards of practice or care may affect conduct of a study and would need to be communicated to research subjects.

• Noncompliance

Noncompliance is a failure to follow the federal regulations with respect to protection of human subjects in research or failure to follow the determinations of the IRB with respect to conduct of the research as approved by the IRB.

Once per year, the IRB is required to review and approve all non-exempt research projects at intervals appropriate to the degree of risk, but not less than once a year. This is called "continuing review." Continuing review for non-exempt research is required to occur as long as the research remains active for long-term follow-up of the research subject, even when the research is permanently closed to the enrollment of new subjects and all subjects have completed all research-related interventions and to occur when the remaining research activities are limited to collection of private identifiable information.

XIII. Data Management:

The following people/agencies may have access to subject data/records:

- Study team
- Federal government regulatory agencies
- Auditing departments of the University of Iowa
- University of Iowa IRB
- Sponsor and/or its representative

To protect confidentiality, we will assign each subject a study ID. All records will be in a locked cabinet in a locked office or password protected computer system. Data and records will be managed as follows:

- Paper/hard copy records (hard copy surveys, questionnaires, case report forms, pictures, etc.) Whenever possible, subject identifying information will be blacked out on all paper or hard copy records and replaced with the subject's unique study identifier. Paper records will be stored in a locked file cabinet in the study team's locked office.
- Electronic records (computer files, electronic databases, etc.) All electronic data bases will only be accessed by the study team and available only with a username and password assigned to study team by the PI.

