- After the completion of the study, all identifiable information will be destroyed according to the University of Iowa's IRB standards, as soon as possible.

XIV. Primary End points:

Performance of Previs device within 18 hours after surgery for predicting subsequent development of gastrointestinal impairment due to ileus.

XV. Payment for Participation:

Subjects will not receive payment for participating in this study. The study related device and study procedures will be paid for by the study.

XVI. Subject Safety:

- To minimize risks all subjects are carefully pre-screened and screened trying to identify any factors that could contribute to increased risk.
- All study procedures are completed at University of Iowa Hospitals and Clinics by a very experienced and well trained staff and monitored by the Principal Investigator.
- All confidential information is kept in locked offices and password protected computers only available to study team members.
- The participant has contact information and study team members available 24/7.

XVII. Statistical design plan:

The definition of post-operative ileus is "the presence of emesis, need for nasogastric intubation, or reversal of the diet beyond 24 hours from the completion of surgery". As the goal of the first phase of this trial is to optimize the device for predicting ileus, we will be maximizing the performance of the device through measurement of sensitivity, specificity, positive predictive value, negative predictive value, AUC, and accuracy of the device for each 10-20 patients (dependent upon the incidence of ileus in each group). The device performance will be compared to the surgeon prediction of ileus development, which will be assessed within the first 24 hours after surgery. The threshold for use in the second phase (validation phase) will be chosen to maximize sensitivity while maintaining the highest possible specificity. Ultimately, device performance will be considered successful if sensitivity higher than that of surgeons can be achieved for predicting ileus.

The study team would like to increase our enrollment plan to 225 patients. We believe that there will be a significant need for pre-optimization where the algorithm is tweaked based upon results in smaller cohorts. Enrollment of 225 patients should allow us an adequate number of cohorts to iteratively pre-optimize the algorithm prior to validation in the final cohort.

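### The device must predict within 18 hours of surgery, but the surgeon it must beat may be asked at any time in the first 24 hours; neither time is fixed and nothing aligns them

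*Protocol*

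**What the plan says.** Protocol section XIV gives the primary endpoint as "Performance of Previs device within 18 hours after surgery for predicting subsequent development of gastrointestinal impairment due to ileus". Section XVII, repeated in the SAP, says that device performance will be "compared to the surgeon prediction of ileus development, which will be assessed within the first 24 hours after surgery". The SAP does not mention the 18-hour limit.

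The only stated success criterion rests on this comparison: "device performance will be considered successful if sensitivity higher than that of surgeons can be achieved for predicting ileus". No margin, test or error rate accompanies it.

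Section X covers the device side in part: "Time and serial number of device application will be logged into study register". It lists no step at which a surgeon is asked for a prediction, and Table 1 has no row for one. The nearest item is the Instrument Questionnaire, given daily in hospital and again later: "Study team member will contact the subject 14 days post-operative to administer Instrument Questionnaire". Its content is not in the documents. Section XIII mentions "hard copy surveys, questionnaires, case report forms, pictures, etc" among the paper records, so a form for the surgeon's prediction may exist.

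**The concern.** A prediction is only as good as the information behind it, and after bowel or bladder surgery that information grows by the hour. To compare the sensitivity of two predictors fairly, both should have had the same length of post-operative observation, or the difference should at least be known. Here the limits themselves differ, and within them either prediction may fall anywhere.

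Two departures are possible, and they pull in opposite directions:

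- **Late surgeon call (18-24 hours).** The surgeon may have seen up to 6 hours more than the device was allowed to use. If that helps the surgeon, the device faces a harder benchmark, and a success claim is conservative.
- **Early surgeon call, device read near 18 hours.** The device has many more hours of data. It could then pass because of timing and not because it predicts better.

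What is at stake is the meaning of the one success criterion. If surgeon times are not required and not used in the analysis, a reader cannot separate the performance of the device from the timing of the question.

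**Working it through.** **1. The two windows, from the documents.**

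| | Earliest | Latest | Source |
|---|---|---|---|
| Device | not fixed | 18 h | Protocol XIV |
| Surgeon | not fixed | 24 h | Protocol XVII; SAP |

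- Difference between the latest permitted times: 24 - 18 = 6 h.
- Share of the surgeon's permitted hours after the device limit: 6/24 = 25%. This is a share of clock time, not of predictions; the documents do not say when surgeons were asked.
- Surgeon time minus device time for one patient: from 0 - 18 = -18 h to 24 - 0 = +24 h.

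**2. What a timing shift could do to the success rule (hypothetical).** The documents give no sensitivity, ileus rate or validation cohort size, so the plan has no figure to reproduce. Assumptions:

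- Device and surgeon are both 60% sensitive at a common time.
- An early or late call moves the surgeon down or up by g = 5 to 10 points.
- There are n = 20 or 40 ileus cases.
- The two counts of correctly predicted cases are independent binomials.

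The rule is met when the device count exceeds the surgeon count:

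P(met) = Σ_k P(D = k) × P(S ≤ k - 1), with D ~ Bin(n, 0.60) and S ~ Bin(n, s).

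If a fraction f of calls is shifted by g, then s = 0.60 ± f × g. For f = 0.25, f × g runs from 0.25 × 5 = 1.25 to 0.25 × 10 = 2.5 points.

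| Scenario | s | n = 20 | n = 40 |
|---|---|---|---|
| Aligned | 0.600 | 0.436 | 0.455 |
| 25% of calls late | 0.6125 to 0.625 | 0.404 to 0.372 | 0.409 to 0.365 |
| All calls late | 0.65 to 0.70 | 0.311 to 0.202 | 0.281 to 0.144 |
| 25% of calls early | 0.5875 to 0.575 | 0.468 to 0.501 | 0.500 to 0.546 |
| All calls early | 0.55 to 0.50 | 0.564 to 0.685 | 0.633 to 0.786 |

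To four places, the aligned value at n = 40 is 0.4546, or 45%. Aligned values are below 50% because a tie does not count as higher.

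**3. Pairing check.** Device and surgeon rate the same patients, so the counts are probably correlated. With an assumed within-patient correlation of 0.3, the aligned values are 0.423 (n = 20) and 0.446 (n = 40). With all calls late they are 0.278 to 0.158 and 0.244 to 0.102; with all calls early, 0.576 to 0.718 and 0.658 to 0.828. The pattern is the same, and the swings are slightly larger.

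**4. Reading.** The wide swings need every call to be early or every call to be late. With a quarter of calls shifted, the chance moves by about 3 to 6 points at n = 20 (for example 0.436 - 0.372 = 0.064) and by about 5 to 9 points at n = 40 (0.455 - 0.365 = 0.090).

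**The case against.** The strongest reply is that the difference in limits is conservative: the surgeon gets up to 6 hours more than the device, which makes success harder. The route to a false success needs surgeons to be asked early. The wording permits that, but nothing says it is planned or usual. This stands as a limit on the claim. A reader might infer that the mismatch favours the device, and the documents do not support that. They do not support the reverse either, since later information need not raise a surgeon's sensitivity.

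A second reply is that 24 hours is a practical window and that both predictions may precede the outcome. A practical window explains flexibility. It does not explain a different limit from the primary endpoint, or the absence of any required time. Even if both predictions precede every event, the predictors can hold different amounts of information.

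Third, a reader might infer that the surgeon's prediction was never recorded or timed. That goes too far. The case report forms are not in these documents, and an early Instrument Questionnaire could carry a surgeon item, although giving it by contacting the subject at day 14 suggests a patient instrument. What can be said is that the plan neither requires nor uses the time.

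Finally, this is a single-centre optimization study, and the threshold is itself tuned: "The threshold for use in the second phase (validation phase) will be chosen to maximize sensitivity while maintaining the highest possible specificity". Threshold choice can drive a win on sensitivality alone whatever the timing. That is true, and it lowers the weight of this point, but it does not remove the confounding by time.

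**Conclusion.** The point holds. The stated limits differ by 6 hours, both are upper limits only, nothing aligns them, and the procedures contain no step for the surgeon's prediction. The success rule can therefore reflect timing as well as device performance.

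The mismatch is certain from the text; its effect is not. The 60% sensitivity, the 5-10 point shift, the case numbers, the correlation and the 25% of shifted calls are all assumptions. A reader might take the all-early or all-late figures as the size of the problem. They are extremes. If a quarter of calls were late, the chance of meeting the rule would fall only from 44% to about 37-40% with 20 ileus cases and from 45% to about 37-41% with 40. Part of that movement comes from a rule with no margin or test, which is a separate matter.

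The change should be made, at the lower end of that grade, because it is cheap and protects the only success criterion. How the ileus events themselves are defined is a separate point and is not judged here.

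**What to change.** **In section XVII and the SAP:** state one common prediction cut-off for device and surgeon, no later than the 18 hours in XIV.

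**In section X and Table 1:** add a step and a row for a yes/no surgeon prediction, time-stamped and recorded without access to device output.

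**For predictions already collected** (the cover page says "We estimate that all subjects will be enrolled by January 2020", before this September 2020 version): keep all patients and the planned comparison. Where the surgeon's time is documented, add a sensitivity analysis that uses device data only up to the earlier of that time and 18 hours. Show results separately for early, late (18-24 hours) and untimed surgeon calls. Treat these groups as descriptive: they may be small, and when a surgeon was asked may depend on other things, such as when the operation ended. The truncated analysis needs device data that can be re-read at an earlier time, which the documents do not confirm.

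Do not restrict the main comparison to surgeon calls in a narrow window ending at 18 hours. That would discard the late, conservative calls, and any gap left inside the window would still favour the device. It would also cost precision: losing 25% of cases widens the confidence interval by about 15% (1/√0.75 = 1.155), and losing 50% by about 41% (1/√0.50 = 1.414).

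**Cost:** wording changes, one form field, one row in Table 1 and a little extra analysis. Surgeons must be asked by the common cut-off, which may be less convenient than any time on the first day.

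### The only success rule compares sensitivity alone and no minimum specificity is set, so a device with no predictive value can be declared successful

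*Protocol*

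**What the plan says.** Protocol Section XVII and the SAP (Statistical Analysis) share the same text on this point.

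- **Success criterion:** "Ultimately, device performance will be considered successful if sensitivity higher than that of surgeons can be achieved for predicting ileus".
- **Threshold rule:** "The threshold for use in the second phase (validation phase) will be chosen to maximize sensitivity while maintaining the highest possible specificity".
- **Measures in the optimisation phase:** the device is tuned "through measurement of sensitivity, specificity, positive predictive value, negative predictive value, AUC, and accuracy of the device for each 10-20 patients".
- **Comparator:** "The device performance will be compared to the surgeon prediction of ileus development, which will be assessed within the first 24 hours after surgery".

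Protocol Section XIV gives the primary end point as "Performance of Previs device within 18 hours after surgery for predicting subsequent development of gastrointestinal impairment due to ileus", with no metric and no minimum value.

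Neither document states a minimum specificity, a specificity margin against surgeons, or a condition on predictive values, AUC or accuracy that enters the verdict.

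**The concern.** Sensitivity can be raised at will by lowering the cut-off, and the price is paid in specificity. A criterion that looks only at sensitivity therefore cannot separate a device that discriminates from one that simply raises the alarm more often than surgeons do.

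The end point is the device's performance in predicting ileus. The verdict uses only how it does in patients who develop ileus and ignores false alarms in those who do not. A device with no information could be labelled successful. An informative one could earn the label at a specificity far below the surgeons'. The other measures might reveal this, but the plan gives them no say in the verdict.

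**Working it through.** The plan states no power, incidence, surgeon accuracy or validation size, so there is no figure of its own to reproduce. The check goes from logic to illustration.

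**1. A device that flags everyone (no assumed inputs needed for the logic).** Sensitivity is 1 and specificity 0. It succeeds unless surgeons identify every case. With n ileus cases and surgeon sensitivity s, P(success) = 1 − sⁿ. Taking n = 20 for illustration:
- s = 0.7: 1 − 0.7²⁰ = 0.999
- s = 0.9: 1 − 0.9²⁰ = 0.88

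At an assumed 20% incidence this device has accuracy and positive predictive value of 20%. Surgeons with assumed sensitivity 50% and specificity 90% would have accuracy 0.2 × 0.5 + 0.8 × 0.9 = 82% and positive predictive value 0.10 / (0.10 + 0.08) = 56%. The device would still be the one called successful.

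**2. A threshold chosen by the plan's rule, sensitivity first.** Read literally, sensitivity is maximised and specificity only separates cut-offs with equal sensitivity. The threshold is then the lowest score among the m training ileus cases. Sensitivity in new cases follows a Beta(m, 1) distribution with mean m/(m + 1), whatever the AUC.

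Assumptions: 20 validation ileus cases, surgeon prediction taken as yes/no, independent device and surgeon calls, success = strictly more cases detected. Then

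P(success) = Σₓ P(X_D = x) · P(X_S ≤ x − 1),

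with X_D beta-binomial(20, m, 1) and X_S binomial(20, s). Specificity is simulated from normal scores with equal variance.

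| m | P(success), s = 0.5 | s = 0.7 | s = 0.9 | Mean specificity, AUC 0.5 | Mean specificity, AUC 0.8 |
|---|---|---|---|---|---|
| 2 | 0.70 | 0.47 | 0.17 | 33% | 69% |
| 4 | 0.89 | 0.69 | 0.29 | 20% | 56% |
| 10 | 0.99 | 0.90 | 0.50 | 9% | 38% |
| 20 | 1.00 | 0.97 | 0.65 | 5% | 28% |

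Values m = 2 to 4 correspond to one cohort of 10–20 patients at 20% incidence. The success probabilities are the same for AUC 0.5 and AUC 0.8. Only specificity differs, and the criterion ignores it.

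**3. The same rule read as a balance.** Take the threshold that maximises Youden's index in 20 ileus and 80 non-ileus training patients. An AUC 0.5 device succeeds with probability about 0.45–0.50 (s = 0.5), 0.26–0.31 (s = 0.7) and 0.08–0.11 (s = 0.9), depending on how ties are broken.

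**4. What a specificity condition does.** Add an illustrative floor of 0.5 on observed specificity in 80 non-cases, with s = 0.5. Success for the AUC 0.5 device falls to 0.05 (m = 2), 0.02 (m = 4) and 0.001 or less (m = 10 and 20) under step 2. Under step 3 it falls to about 0.05–0.06.

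**The case against.** The strongest reply has four parts.

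- **The threshold rule protects specificity, and reducing that clause to a tie-breaker is uncharitable.** It is fair that the largest probabilities, and the finding that success does not depend on AUC, belong to the sensitivity-first reading. Under the balanced reading the figures are lower. But neither reading sets a minimum, and specificity stays outside the success sentence.
- **Part of the balanced-reading figure is chance.** This stands. Two predictors with sensitivity near 0.5 will each come out ahead nearly half the time, because the plan has no test or confidence interval. Those figures cannot be attributed wholly to the missing specificity term.
- **Specificity, predictive values, AUC and accuracy are measured, so a flag-everyone device would be exposed.** It would be, if they are also reported for validation. The defect lies in the pre-specified verdict, not in what the trial can learn. The measures are listed for tuning and carry no weight in that verdict.
- **This is a single-centre optimisation study in which participation does not alter standard care, and favouring sensitivity in an early warning is a legitimate choice.** Both points limit the harm. A preference for sensitivity can still be expressed through a generous margin; it does not call for ignoring specificity altogether.

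Independence of device and surgeon calls is exact for an uninformative device. It is doubtful for the AUC 0.8 and 0.9 figures, where both may recognise the same patients.

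**Conclusion.** The concern holds. Followed exactly as written, the criterion labels a device with no predictive value successful whenever it flags everyone and surgeons miss one case. This rests on the wording alone.

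The probabilities are illustrations. They assume 20 validation ileus cases, yes/no surgeon predictions and a range of surgeon sensitivities, none of which the documents supply. Across those assumptions, false success for an AUC 0.5 device runs from about 0.08 (balanced threshold, surgeon sensitivity 0.9) to almost 1 (sensitivity first, 20 training cases, surgeon sensitivity 0.5). Because this is the trial's only success criterion, it should be corrected before it is applied.

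**What to change.** Make these changes in both Protocol Section XVII and the SAP, before validation data are examined:

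1. Replace the success sentence with, for example: *The device meets its success criterion if, in the validation cohort and at the threshold fixed in advance, its sensitivity exceeds the surgeons' and its specificity is no more than [margin] below theirs.* State the margin. A very wide margin would bring the problem back.
2. Choose the threshold in the optimisation data as the one with the highest sensitivity that meets the same specificity constraint. State whether the training target sits at the margin or nearer to surgeon specificity.
3. Record the surgeon prediction as yes/no, or give its cut-off in advance.

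**Cost.** This is wording only. Surgeon specificity comes from predictions and outcomes the planned comparison already uses. Success becomes harder to claim, and the sponsor must choose the margin. If surgeons rarely predict ileus, their specificity will be near 100% and the margin must allow for that.

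The training target matters. The table gives the probability of success assuming surgeon sensitivity 0.5 and specificity 0.8, margin 0.10, 80 training non-cases, and 20 ileus and 80 non-ileus validation patients, compared on observed values.

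| Training specificity target | AUC 0.9 | AUC 0.8 | AUC 0.5 |
|---|---|---|---|
| At the margin (0.70) | 0.49 | 0.45 | 0.03 |
| Half the margin (0.75) | 0.72 | 0.61 | 0.03 |
| Surgeon specificity (0.80) | 0.87 | 0.67 | 0.02 |

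The protocol is dated September 2020 but estimates that enrolment ends by January 2020, so validation may already have begun. If its results have been seen, the margin should be labelled as chosen afterwards, and device and surgeon specificity reported beside any claim of success.

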Cover Page for Statistical Analysis Plan

Sponsor-Investigator:	[name]
NCT Number:	NCT03505476
Unique Protocol ID:	201801808
Official Title:	Optimizing the Previs Device for Prediction of Postoperative Ileus
Date of Document:	11 December 2018

Statistical Analysis

The definition of post-operative ileus is "the presence of emesis, need for nasogastric intubation, or reversal of the diet beyond 24 hours from the completion of surgery". As the goal of the first phase of this trial is to optimize the device for predicting ileus, we will be maximizing the performance of the device through measurement of sensitivity, specificity, positive predictive value, negative predictive value, AUC, and accuracy of the device for each 10-20 patients (dependent upon the incidence of ileus in each group). The device performance will be compared to the surgeon prediction of ileus development, which will be assessed within the first 24 hours after surgery. The threshold for use in the second phase (validation phase) will be chosen to maximize sensitivity while maintaining the highest possible specificity. Ultimately, device performance will be considered successful if sensitivity higher than that of surgeons can be achieved for predicting ileus.

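### The only success rule, device sensitivity above that of surgeons, has no test, confidence interval or specificity condition, so a device no better than surgeons can readily be declared successful

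*Protocol*

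**What the plan says.** Protocol section XVII gives the success rule: "Ultimately, device performance will be considered successful if sensitivity higher than that of surgeons can be achieved for predicting ileus". It recurs in the SAP's Statistical Analysis text: "device performance will be considered successful if sensitivity higher than that of surgeons can be achieved for predicting ileus". The comparator is described as follows: "The device performance will be compared to the surgeon prediction of ileus development, which will be assessed within the first 24 hours after surgery". The natural reading is that device and surgeon are scored on the same patients, so the data are paired.

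Specificity appears in two places. It is one of six performance measures computed in each small optimization group, and it enters the choice of cut-off: "The threshold for use in the second phase (validation phase) will be chosen to maximize sensitivity while maintaining the highest possible specificity". Neither place sets a floor, compares specificity with that of surgeons, or makes it a condition of success.

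Section XVII describes tuning in successive cohorts, to "iteratively pre-optimize the algorithm prior to validation in the final cohort", but gives no size for that final cohort. The total also differs within the protocol. The front matter says "475 subjects (50% male, 50% female) will be recruited and enrolled in this study", while section XVII says "The study team would like to increase our enrollment plan to 225 patients". Neither total is divided between tuning and validation. The primary endpoint in section XIV is device performance, with no metric attached.

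**The concern.** Because the primary endpoint names no metric, the sensitivity sentence is the only rule in either document that separates success from failure. Read literally, it is met when the device detects one more ileus patient than the surgeons did. There is no allowance for chance, so equal performers are separated by luck.

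The rule is also one-sided in what it counts. Sensitivity can always be raised by lowering the cut-off, at the price of false alarms. A rule that counts only sensitivity cannot fail a device that flags almost everyone. At stake is a claim that the device predicts ileus better than surgeons, made on data that could equally have come from a device that is no better or carries no information.

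**Working it through.** **Inputs from the documents.** The rule, the paired comparator, and totals of 475 and 225. No alpha, power, effect size, incidence, surgeon sensitivity or validation size is stated, so the plan has no figure to reproduce. The only cohort size mentioned is 10-20 patients, for optimization.

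**Assumptions.** True sensitivity s = 0.5-0.8; correlation ρ between device and surgeon errors 0-0.3; threshold fixed before validation; m ileus cases in validation. For scale:
- 20 patients at 20% incidence give 20 × 0.2 = 4 cases.
- All 225 patients at 10-30% give 22.5-67.5 cases.
- All 475 at 10-30% give 47.5-142.5 cases.

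The last two lines leave nobody for tuning, so they are upper bounds for each total.

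**Equally sensitive device.** In each ileus case, the probability that only the device is right equals the probability that only the surgeon is right: s(1−s)(1−ρ). The number of discordant cases K is binomial with m trials and probability 2s(1−s)(1−ρ). A tie is not a pass, so by symmetry

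P(pass) = [1 − P(tie)]/2, with P(tie) = Σ over even k of P(K=k)·C(k, k/2)/2^k.

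Example, s = 0.7 and ρ = 0: each direction is 0.7 × 0.3 = 0.21, so the discordant probability is 0.42.
- m = 4: P(tie) = 0.303, P(pass) = 0.349.
- m = 10: P(tie) = 0.193, P(pass) = 0.403.
- m = 50: P(tie) = 0.087, P(pass) = 0.457.

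**Device that calls 95% positive at random.** Its sensitivity is 0.95 and its specificity 0.05, whatever the patient's outcome. Its calls are independent of the surgeon's, and P(pass) is the probability that it has more sole detections than the surgeon.

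| Ileus cases | Equal device passes (s 0.5-0.8, ρ 0-0.3) | 95%-positive device passes, surgeon at 0.5 / 0.8 |
|---|---|---|
| 4 | 0.273-0.363 | 0.886 / 0.512 |
| 10 | 0.363-0.412 | 0.990 / 0.757 |
| 45 | 0.437-0.458 | 1.000 / 0.982 |
| 50 | 0.440-0.460 | 1.000 / 0.987 |
| 142 | 0.465-0.476 | not computed |
| 500 | 0.481-0.487 | not computed |

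The equal device's rate is lower in small cohorts only because ties are common there. More cases push it towards 0.5, so a larger cohort does not cure the problem. A device that is truly worse, 0.6 against 0.7, passes 8-13% of the time at 45-50 cases.

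**Would a test on sensitivity alone be enough?** With a two-sided exact McNemar test at p<0.05 in the device's favour and 50 cases, the equal device passes 1.2-1.5% of the time and the 0.6-versus-0.7 device less than 0.1%. The 95%-positive device still passes 52-100% of the time. If surgeon specificity is assumed to be 0.7-0.9, that device's specificity difference is 0.05 − 0.7 = −65 points to 0.05 − 0.9 = −85 points, so a paired specificity condition rejects it. Both conditions are needed.

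**The case against.** The strongest defence is the nature of the study. It is a single-center, open-label prototype study whose stated aims are redesign and refinement, superiority to surgeons is not among those aims, and no error rate is claimed. The sentence could be read as a development milestone. This does not carry the point, because section XVII itself names a validation phase, a final validation cohort and a success claim against surgeons. A validation rule should be able to fail an uninformative device.

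Several parts of the defence do stand:
- **Magnitude.** A reader might infer that an equal device passes almost half the time as a property of the plan. The documents do not support that as a flat statement, because it needs some tens of ileus cases and they give no validation size or incidence.
- **Near-certain success for an indiscriminate device.** This too is a result for larger cohorts. With 4 cases and surgeons at 0.8 it is about an even chance.
- **Specificity.** It would be wrong to infer that the plan ignores it. The cut-off is meant to keep specificity as high as possible, which steers away from an indiscriminate device. It sets no floor, however, and does not enter the success rule.
- **Separation of tuning and validation.** A reader might infer that success will be judged on tuning data. The text places validation after tuning, in a final cohort. What is missing is an explicit freeze and exclusion of tuning patients.

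**Conclusion.** The defect is real and should be corrected before the validation data are examined. Both documents make a bare comparison of sensitivities the sole criterion, and followed as written it can declare an equally sensitive or uninformative device better than surgeons. Confidence in that structural point is high.

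Confidence in the size is moderate, because case count, surgeon sensitivity and error correlation are all assumed. Over 4 to 142 cases, the equal device's chance of success runs from roughly 27% to 48%. It is far above a conventional error rate throughout, so the conclusion does not depend on which case count applies.

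**What to change.** In section XVII and the SAP:

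1. State that success is judged only in the final validation cohort, with algorithm and threshold frozen beforehand and no patients used in tuning. Reconcile 475 with 225 and state the validation size.
2. Declare success only if a two-sided exact McNemar test among ileus patients favours the device at p<0.05. Report the paired sensitivity difference with its 95% CI.
3. Require also that the lower 95% limit of the paired device-minus-surgeon specificity difference, in patients without ileus, lies above a largest acceptable loss. The sponsor states that loss before the validation data are examined.
4. State, also before the validation data are examined, the minimum number of ileus cases needed for a superiority claim. Below it, report both paired differences with CIs and make no such claim. Some minimum is unavoidable: five discordant pairs all favouring the device give p = 2 × 0.5^5 = 0.0625, so at least six are needed (2 × 0.5^6 = 0.031).

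**Cost.** The change is wording plus a routine paired analysis. No extra patients are required, but only because item 4 allows the claim to be dropped. The downside is limited power. Assume 50 ileus and 200 non-ileus patients (250 in all, more than the 225 in section XVII), equal true specificity of 0.8, and correlation 0 or 0.3. McNemar power is 0.498 or 0.661 for sensitivity 0.8 versus 0.6, and 0.149 or 0.192 for 0.8 versus 0.7. The specificity condition is met with probability 0.707 or 0.847 for an illustrative 10-point loss, and 0.963 or 0.994 for 15 points. The two conditions use different patients, so the probabilities multiply:

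- 0.8 versus 0.6, 10 points: 0.498 × 0.707 = 0.352 to 0.661 × 0.847 = 0.560.
- 0.8 versus 0.6, 15 points: 0.498 × 0.963 = 0.480 to 0.661 × 0.994 = 0.657.
- 0.8 versus 0.7, 10 points: 0.149 × 0.707 = 0.105 to 0.192 × 0.847 = 0.163.

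Equal specificity is an optimistic assumption when the cut-off favours sensitivity, so actual power may be lower.
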